Lung cancer is the leading cause of cancer death in the US and worldwide. In 2011, approximately 221,130 new cases of lung or bronchial cancer were expected to be diagnosed in the US, and 156,940 patients (71%) are estimated to die of this disease (Siegel *et al.*, 2011). Approximately 64% of non-small-cell lung cancer (NSCLC) patients and 54% of small-cell lung cancer (SCLC) patients will require radiotherapy at least once (Tyldesley *et al.*, 2001). Stereotactic body radiotherapy (SBRT) has provided excellent clinical outcomes for early stage NSCLC, e.g., three-year local control, 98%; three-year survival, 56% in the Radiation Therapy Oncology Group (RTOG) 0236 trial (Timmerman *et al.*, 2010). For advanced stage NSCLC, however, Machtay *et al.* have recently reported a five-year survival rate of 15% for patients treated with chemoradiotherapy from seven RTOG trials (Machtay *et al.*, 2012). The maximum tolerated dose is limited by the risk of toxicity, especially for advanced disease. For example, an attempt to escalate the prescribed dose in the early Phase I portion of RTOG 0117 was unsuccessful because of severe toxicity, including Grade 3 and 5 radiation pneumonitis (Bradley *et al.*, 2005b). Radiation pneumonitis is a common, potentially fatal toxicity that occurs in 5-30% of lung cancer patients treated with radiotherapy (Marks *et al.*, 2010; Palma *et al.*, 2013).

1.2. Personalized radiotherapy that avoids high-functional lung regions may reduce toxicity and facilitate safe investigations designed to improve tumor control

To address the critical problem described above, we propose a novel paradigm, *i.e.*, functional image-guided personalized radiotherapy that avoids high-functional lung regions. It may reduce toxicity and facilitate safe investigations designed to improve tumor control. This hypothesis is supported by several findings in the literature. Abratt *et al.* have found that patients whose irradiated lung regions had >35% of the total lung perfusion are significantly more likely to manifest post-treatment decreases in diffusing capacity and worsening of dyspnea score (Abratt *et al.*, 1990). Seppenwoolde *et al.* (Seppenwoolde *et al.*, 2004) and Vinogradskiy *et al.* (Vinogradskiy *et al.*, 2013) have demonstrated better correlations between the function-weighted lung dose and pneumonitis than those between the physical lung dose and pneumonitis.

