2.2. Secondary objectives

- 1) Assess long-term toxicity from 4D CT ventilation image-guided personalized radiotherapy as scored by the NCI-Common Terminology Criteria for Adverse Events (CTCAE) version 4.0.
- 2) Estimate the clinical significance of 4D CT ventilation image-guided personalized radiotherapy by evaluating: (1) clinical and subclinical endpoints for pulmonary toxicity (including symptomatic radiation pneumonitis and post-treatment changes in pulmonary function tests (PFTs), 6-min walk test, and BODE index); (2) correlation between those endpoints and functional dose-volume parameters.
- 3) Assess local tumor control after 4D CT ventilation image-guided personalized radiotherapy.
- 4) Quantify the dosimetric significance of 4D CT ventilation image-guided adaptive radiotherapy.

- 5) Investigate whether in vivo EPID dosimetry can detect clinically significant anatomic changes for patients treated with CFRT.

3. Patient Selection

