5.4.2. Lungs

We will create 4D CT ventilation image-guided personalized radiotherapy plans that selectively avoid irradiating highly-functional lung regions. The peak-inhale 4D CT ventilation image will be aligned with the free-breathing CT image (primary image set for treatment planning) by rigid image registration. The overlapped lungs between the free-breathing CT and peak-inhale 4D CT images will be contoured. Note that the final total lung volume for dose-volume analysis will include combined right and left lungs, excluding the GTV, trachea, and main and lobar bronchi. IMRT or VMAT optimization will be performed by setting higher weights to highly-functional lung regions than poorly-functional regions to meet the dose-volume constraints shown below.

CFRT

Tissue	Constraints
Lung (right and left minus CTV)	$V_{20} < 37\%$ (<40% will be scored as a minor deviation) Mean lung dose (MLD) <20 Gy (<21 Gy will be scored as a minor deviation) Functional $V_{20} < 30\%$ (Vinogradskiy et al. , 2013) (<33% will be scored as a minor deviation) Functional MLD <19 Gy (Vinogradskiy et al. , 2013) (<20 Gy will be scored as a minor deviation)

SABR

Tissue	3 fraction			5 fraction		
	Volume	Vol Max	Max to 0.03 cc	Volume	Vol Max	Max to 0.03 cc
Lung (right and left minus CTV)	<1500 cc	10.5 Gy*	NA	<1500 cc	12.5 Gy*	NA
	<1000 cc	11.4 Gy*		<1000 cc	13.5 Gy*	
	Functional $V_{20} < 4\%$ (Barriger et al. , 2012) (<7% will be scored as a minor deviation) Functional MLD <4 Gy (Barriger et al. , 2012) (<5 Gy will be scored as a minor deviation)					

*Constraints marked by asterisk are guidelines and will not be scored as a protocol deviation if not achieved. For SABR in patients with more than one target, the lung dose-function constraints (functional MLD and V20) are guidelines and will not be scored as a protocol deviation if not achieved. **Other constraints represent absolute limits and treatment delivery that cannot meet these constraints will constitute a major protocol violation.**

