9.1. Study endpoints

Primary endpoints

(1) Grade ≥ 3 radiation pneumonitis, (2) grade ≥ 3 esophagitis, (3) other grade ≥ 3 AEs that occur ≤ 12 months after treatment and drop-out defined as definitely, probably, or possibly related to the protocol treatment.

Secondary endpoints

- 1) Long-term toxicity, as scored by the NCI-CTCAE version 4.0.
- 2) Clinical and subclinical endpoints for pulmonary toxicity (including radiation pneumonitis and post-treatment changes in PFTs, 6-min walk test, and BODE index).
- 3) Correlation between the clinical/subclinical endpoints for pulmonary toxicity and functional dose-volume parameters.

- 4) Local tumor control.
- 5) Lung functional dose-volume metrics, including the functional V_x (fV_x) (% volume receiving $\geq x$ Gy) and functional mean lung dose (fMLD).

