9.3. Analysis plan

Primary endpoints: (1) Grade ≥ 3 radiation pneumonitis, (2) grade ≥ 3 esophagitis, (3) other grade ≥ 3 AEs that occur ≤ 12 months after treatment and drop-out defined as definitely, probably, or possibly related to the protocol treatment.

We will estimate the rates of AEs and tolerability with exact 95% confidence intervals. 4D CT ventilation image-guided personalized radiotherapy will be considered safe if AE rates are lower than the following acceptable rates (determined based on the published toxicity data for locally advanced lung cancer patients): (1) grade ≥ 3 radiation pneumonitis, 13% (Jiang *et al.*, 2012), (2) grade ≥ 3 esophagitis, 21% (Wei *et al.*, 2006), and (3) other grade ≥ 3 AEs and drop-out, 20% (Bradley *et al.*, 2015).

Secondary endpoints

Analyses of secondary endpoints will be primarily descriptive rather than hypothesis testing.

Toxicity will be summarized by frequency and exact 95% confidence intervals, overall and separately by grade and organ system.

The clinical significance of 4D CT ventilation image-guided personalized radiotherapy will be estimated by evaluating: (1) clinical and subclinical endpoints for pulmonary toxicity (including radiation pneumonitis, PFTs, 6-min walk test, and BODE index); (2) correlation between those endpoints and functional dose-volume parameters. Radiation pneumonitis will be assessed at follow-up every 3 months for a minimum of 2 years after treatment using the NCI-CTCAE version 4.0. Post-treatment changes in PFTs (including spirometry, lung volumes and diffusing capacity), 6-min walk test, and the BODE index will be evaluated at the time of 6-month follow-up. Using composite treatment plans, the following lung functional dose-volume parameters will be calculated: functional mean lung dose (fMLD), functional V_{20} (fV_{20}) and functional effective dose (fD_{eff}) (Vinogradskiy *et al.*, 2013), which will be correlated with the endpoints for pulmonary toxicity.

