To quantify the dosimetric significance of 4D CT ventilation image-guided adaptive radiotherapy, we will create: (1) 4D CT ventilation image-guided adaptive radiotherapy plan, (2) 4D CT ventilation image-guided non-adaptive radiotherapy plan, and (3) anatomical image-guided non-adaptive radiotherapy plan. We will evaluate the lung functional dose-volume parameters, including the functional V_x (fV_x) (% volume receiving $\geq x$ Gy) and functional mean lung dose (fMLD) for each plan. The lung functional dose-volume parameters of the 4D CT ventilation image-guided adaptive radiotherapy plans will be compared with those of the 4D CT ventilation image-guided non-adaptive radiotherapy plans and anatomical image-guided non-adaptive radiotherapy plans using a paired *t*-test. Furthermore, we will also investigate sensitivity to the number (1 or 2) and time (16-20 Gy and/or 30-34 Gy) of plan adaptation to design an optimal adaptive radiotherapy strategy, *e.g.*, when and how many time(s) to adapt the original plan.

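### The lung-toxicity correlations use functional dose only; without the physical-dose counterparts they cannot show that ventilation weighting adds anything

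*Combined protocol and SAP*

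**What the plan says.** Secondary objective 2 (Section 2.2) is to estimate clinical significance in two parts: (1) the pulmonary endpoints themselves, and (2) the "correlation between those endpoints and functional dose-volume parameters". Section 9.1 lists the same item as secondary endpoint 3: "Correlation between the clinical/subclinical endpoints for pulmonary toxicity and functional dose-volume parameters".

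Section 9.3 carries this out. fMLD, fV20 and fDeff are taken from composite treatment plans, "which will be correlated with the endpoints for pulmonary toxicity". The same section describes the secondary analyses as mainly descriptive. It sets no alpha, power or effect size for the correlations.

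The motivation is comparative. Section 1.2 cites two earlier studies as showing "better correlations between the function-weighted lung dose and pneumonitis than those between the physical lung dose and pneumonitis". Section 1.4 assumes that pneumonitis rises with dose to high-functional lung much as published data show for dose to the whole lung.

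Physical lung dose appears in the CFRT constraint table of Section 5.4.2 ("Mean lung dose (MLD) <20 Gy", with a V20 limit), next to the functional limits ("Functional MLD <19 Gy", with a functional V20 limit). It is not mentioned in the toxicity analysis.

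**The concern.** fMLD is a re-weighted average of the same dose distribution over the same lungs as MLD. A patient with a high MLD will usually have a high fMLD. If physical lung dose alone caused the toxicity, fMLD would still correlate with it. The planned analysis gives a similar answer whether or not ventilation weighting carries information.

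What is at stake is how part (2) of secondary objective 2 can be interpreted. The question raised by the rationale is whether functional dose tracks toxicity better than physical dose. The planned output has nothing to set the functional correlation against, although the physical values can be obtained from dose distributions the trial already holds.

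**Working it through.** **Is a physical-dose comparator planned anywhere?**

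- Sections 2.2, 9.1 and 9.3 name functional parameters only.
- No section correlates toxicity with physical MLD, V20 or effective dose, adjusts for physical dose, or compares the two kinds of predictor.
- The anatomical plan in Section 9.3 does not fill the gap. It is compared with the ventilation-guided adaptive plan on functional dose parameters by paired t-test, with no toxicity outcome.

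**Plan's own figures.** None are given for the correlations. The number evaluable has to come from Section 9.4, which starts from 20 patients and enrols 34 to cover 38% loss.

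- 20/(1 − 0.38) = 32.3, so 33, close to the stated 34.
- The stated 94% chance of at least one grade ≥3 pneumonitis also fits 20 patients: 1 − 0.87^20 = 93.8%.

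I therefore use n = 20 as the plan's working number. As a more generous figure for the 6-month endpoints I use 34 × √0.63 = 27.0. This takes the plan's 37% one-year mortality at constant hazard and assumes every survivor is measured.

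**Illustration. Assumed inputs, not from the documents:**

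- continuous 6-month endpoint, driven by physical MLD only, true r = 0.40;
- corr(fMLD, MLD) = ρ, from 0.80 to 0.95;
- fMLD has no effect of its own.

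**Formulas.** Expected fMLD correlation r_f = 0.40 × ρ. Fisher z = atanh(r_f), with standard error 1/√(n − 3). Probability of nominal two-sided p < 0.05 ≈ Φ(z√(n − 3) − 1.96); the opposite tail is negligible.

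| ρ | r_f | z | n = 20 (√17 = 4.123) | n = 27 (√24 = 4.899) |
|---|---|---|---|---|
| 0.80 | 0.32 | 0.332 | Φ(−0.59) = 28% | Φ(−0.34) = 37% |
| 0.90 | 0.36 | 0.377 | Φ(−0.41) = 34% | Φ(−0.11) = 45% |
| 0.95 | 0.38 | 0.400 | Φ(−0.31) = 38% | Φ(0.00) = 50% |

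At a lower overlap, ρ = 0.70, r_f = 0.28 and the probabilities are 22% and 29%. In every row ventilation weighting adds nothing.

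**What could a comparator show?** Reverse the roles, so that fMLD is the true driver, and test the difference between the two dependent correlations (Williams test, 20,000 simulated trials per scenario). With r = 0.5 to 0.6 and ρ = 0.70 to 0.95, power to show that fMLD beats MLD is about 7% to 21% at n = 20 and 8% to 35% at n = 34. With r = 0.40 and ρ = 0.80 to 0.95, the expected difference is only 0.40 × (1 − ρ) = 0.08 to 0.02. Grade ≥3 pneumonitis offers little more: at 13%, 2.6 events are expected in 20 patients and 4.4 in 34.

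**The case against.** The strongest reply is that the analysis is secondary and descriptive, and no claim or decision is tied to it. The comparative statement in Section 1.2 is background, and showing that functional dose outperforms physical dose is not a listed objective. This stands as a limit on severity. It does not remove the point: a descriptive fMLD correlation with nothing beside it has the same ambiguity as a tested one, and the plan uses it to estimate clinical significance.

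A second reply is that the illustration rests on assumed inputs. This is true. The optimiser deliberately weights functional and non-functional lung differently, so the overlap could be below 0.80. The significance test being counted is not planned. The 37% mortality comes from locally advanced disease, while the trial also admits SABR patients. The walk test is optional and BODE depends on it, so fewer than 27 may be measured. The percentages show scale only; the logical gap does not depend on them. Pooling would push the other way: Section 9.3 states no split by modality, and the functional MLD limits (19 Gy for CFRT, 4 Gy for SABR) suggest that pooled functional and physical dose would move together.

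A third reply is that the comparison is underpowered. This is also true, and it rules out making the difference a pass/fail test. It is no reason to leave the physical correlations out.

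**Conclusion.** The omission is real. A functional correlation alone cannot separate an effect of ventilation weighting from the whole-lung dose effect that Section 1.4 itself relies on. Under the stated assumptions, a correlation of 0.32 to 0.38 would be expected with no contribution from weighting, nominally significant in 28% to 38% of trials at 20 patients and 37% to 50% at 27.

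The reach is limited to part (2) of secondary objective 2. Part (1), the endpoints themselves, and the primary safety conclusion are unaffected.

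Three stronger readings are tempting, and the documents do not support them:

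- *The investigators will present a positive correlation as proof of functional avoidance.* No section says so.
- *Secondary objective 2 as a whole cannot be interpreted.* Its first part does not use the correlations.
- *Only a demonstrated advantage over physical dose should count as support.* With power of roughly 7% to 35%, such a rule would usually fail even if functional dose were the true driver.

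This is a cheap improvement of low severity.

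**What to change.** In Section 9.3:

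- Calculate unweighted MLD, V20 and Deff from the same composite plans for all patients.
- For each pulmonary endpoint, report each physical correlation next to its functional counterpart, with the difference and a 95% CI from a bootstrap over patients. Label this descriptive and exploratory.
- State that a functional correlation on its own does not show added value of function weighting.
- State that the trial has low power to separate the two, so a difference near zero is inconclusive and is not evidence against function weighting.
- Do not make the difference a binding criterion.

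Cost: a few sentences and a little extra dose extraction. Physical MLD and V20 are constraints for CFRT plans only, so they must be extracted for SABR plans, and physical Deff, which the plan does not mention, must be calculated for everyone. No new patient data are needed. The likely downside is a less favourable statement with wider intervals.

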5.1. Dose specifications

CFRT

Patients undergoing CFRT will receive a total of 60 Gy in 30 fractions. The plan will be normalized such that $\geq 95\%$ of the PTV receives the prescription dose. Minimum dose to the PTV (defined as the dose to the lowest 0.03 cc) must be $\geq 90\%$ of the prescription dose ($\geq 85\%$ will be scored as a minor deviation) and maximum dose must be $\leq 115\%$ of the prescription dose to ≤ 0.03 cc ($\leq 120\%$ will be scored as a minor deviation).

SABR

Patients undergoing SABR will receive a total of 54 Gy in 3 fractions for peripheral tumors or 55 Gy in 5 fractions for centrally located tumors (defined as within 2 cm of the proximal bronchial tree or PTV touching mediastinal structures or pleura; tumors with significant chest wall overlap of PTV can also be treated over 5 fractions at treating physician discretion). The prescription isodose surface will be chosen such that 95% of the target volume (PTV) is conformally covered by the prescription isodose surface and 99% of the target volume (PTV) receives a minimum of 90% of the prescription dose.

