5.4. Treatment planning

Treatment plans will be created using a research version and a clinical version of the Pinnacle treatment planning system (Philips Radiation Oncology Systems, Fitchburg, WI). The research version has not received regulatory clearance, whereas the clinical version has a FDA 510(k) clearance and is routinely used for treatment planning in the Department of Radiation Oncology. First, the research version will be used to create an initial 4D CT ventilation image-guided treatment plan. The initial plan will then be transferred to the clinical version for final dose calculation and evaluation by a radiation oncologist to ensure that the plan quality is clinically appropriate, i.e., target coverage is adequate and critical structures are spared as necessary.

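### The three-plan comparison scores only functional lung dose, so trade-offs in target coverage or other organs within the protocol's limits would not be seen

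*Combined protocol and SAP*

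**What the plan says.** Secondary objective 4 (Section 2.2) is broad: "Quantify the dosimetric significance of 4D CT ventilation image-guided adaptive radiotherapy". The endpoint and the analysis are narrower. Secondary endpoint 5 (Section 9.1) reads "Lung functional dose-volume metrics, including the functional" Vx and functional mean lung dose. Section 9.3 lists three plans, the last being "3) anatomical image-guided non-adaptive radiotherapy plan", and then says "We will evaluate the lung functional dose-volume parameters", again naming fVx and fMLD. The adaptive plans are to be compared with the ventilation-guided non-adaptive plans and with "anatomical image-guided non-adaptive radiotherapy plans using a paired *t*-test". The same section goes on to vary the number and timing of adaptations in order to choose an adaptive strategy, and it names no further metric for that choice.

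On how plans are made, Section 5.4.2 describes optimisation by "setting higher weights to highly-functional lung regions than poorly-functional regions", subject to a table of lung constraints. Section 5.4 has a radiation oncologist confirm that "target coverage is adequate and critical structures are spared as necessary". Section 5.1 fixes the CFRT normalisation: "The plan will be normalized such that" at least 95% of the PTV gets the full prescription.

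**The concern.** Functional avoidance moves dose. When highly functional lung is given more weight, dose can shift into poorly functional lung or other tissue, or target coverage can change. The planned comparison looks at the quantity the optimiser was asked to lower and at nothing that might have been given up for it.

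Two things are at stake. First, objective 4 would be answered with one side of the trade-off. Second, the choice of how often and when to adapt would rest on functional lung dose alone. Clinical outcomes cannot supply the other side, because adverse events cannot be attributed to plans that were never delivered.

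**Working it through.** Section 9.3 gives no sample size, standard deviation or target difference for this comparison, so there is no figure to reproduce. The check sets the passages side by side.

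**1. What is constrained and what is compared.** Mid-treatment scans are taken for CFRT only (Section 4.1), so the CFRT limits from Sections 5.1, 5.4.2 and 5.4.3 are used.

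| Quantity | Rule in Section 5 (CFRT) | Compared between plans in 9.3? |
|---|---|---|
| Functional MLD | <19 Gy (minor deviation <20 Gy) | Yes |
| Functional V20 | <30% (minor deviation <33%) | Yes, as one of the fVx |
| Total-lung MLD | <20 Gy (minor deviation <21 Gy) | No |
| Total-lung V20 | <37% (minor deviation <40%) | No |
| PTV | ≥95% receives prescription; minimum ≥90%, maximum ≤115%, each with a minor-deviation band | No |
| Esophagus | Maximum 70 Gy; mean <34 Gy as a guideline only | No |
| Heart | Maximum 70 Gy; 60 Gy to <33%, 45 Gy to <66% | No |
| Spinal cord | Maximum 47 Gy | No |

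The compared metrics are also the ones that ventilation-guided plans are built to improve. The remaining rows are limited but not compared.

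**2. What a pass/fail limit leaves open.** Let *m* be the total MLD of a patient's anatomical plan. A ventilation-guided plan meets the constraint at any total MLD below 20 Gy. A rise of up to 20 − *m* Gy therefore causes no deviation, and a rise of up to 21 − *m* Gy causes only a minor one. For total-lung V20, with anatomical value *v*, the corresponding room is 37 − *v* and 40 − *v* percentage points. The documents give neither *m* nor *v*. The room is near zero if the anatomical plan already sits at the limit and several Gy if it sits well below. For esophagus mean dose, exceeding the guideline is not scored, so that rule sets no binding ceiling.

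**3. Which plans the rules cover.** Section 5.4.2 applies the lung constraints when ventilation-guided plans are created, which on a natural reading covers both the adaptive and the non-adaptive ventilation-guided plan. The statement that the other constraints are absolute is worded for treatment delivery. The oncologist review in Section 5.4 is described for the ventilation-guided treatment plan. No section says that the anatomical comparison plan shares the PTV normalisation or the non-functional constraints. If it does not, part of an fMLD difference could reflect different coverage, in either direction.

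**4. How far the result is built in.** Ventilation-guided versus anatomical sets a plan optimised on function against one that is not, so an advantage on fMLD and fVx is largely expected by construction. Adaptive versus non-adaptive sets two ventilation-guided plans against each other, so the argument is weaker there. The missing information on other structures applies to both contrasts.

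**The case against.** The strongest reply is that the protocol already limits the harm. PTV coverage, minimum and maximum are fixed. Total-lung V20 and MLD, heart, cord and esophagus maximum are constrained. The lung constraints apply when ventilation-guided plans are made, and an oncologist reviews the treatment plan. Section 9.3 also calls the secondary analyses mainly descriptive and sets no threshold or superiority rule.

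Much of this stands. A reader might infer that any gain in functional dose would be reported as pure benefit whatever it cost elsewhere. The documents do not support that: a gross loss of coverage or sparing would breach Section 5, and no text claims benefit from fMLD alone. A reader might also infer that the whole paired test is a foregone conclusion. That fits at most the contrast with the anatomical plan.

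Nor does the esophagus gap weaken primary endpoint 2. Esophagitis is observed in treated patients and judged against a 21% rate, independently of the plan comparison.

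The limits still show only that a plan is acceptable. They do not show how two acceptable plans differ. A descriptive analysis that informs the choice of adaptation strategy should show both sides.

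**Conclusion.** The point holds in a limited form. As written, the comparison reports functional lung metrics only. Trade-offs inside the Section 5 limits, or coverage differences if the anatomical plan is made under other rules, would not appear in the planned result. This narrows what objective 4 can conclude and affects the choice of number and timing of adaptations. It does not touch the primary safety conclusion.

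No numerical size can be given. A reader might try to turn an assumed rise in total MLD into lost benefit, using the Section 1.4 equivalence of 2 Gy less to high-functional lung and 4% less pneumonitis. The documents do not support that calculation. The relation is borrowed from total-lung data to stand in for high-functional lung dose. Total lung includes high-functional lung, so applying the slope to both and subtracting uses it twice. The 2 Gy concerns functional versus anatomical planning, not adaptation, and no document gives a figure for any rise in total MLD.

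The conclusion rests on reading the lists in Sections 9.1 and 9.3 as confined to functional lung metrics. Both say that the list includes fVx and fMLD, which leaves room for other functional metrics but not for other structures.

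**What to change.** In Section 9.1 (endpoint 5) and Section 9.3:

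- State that all plans being compared, including the anatomical one, are generated under the same prescription, PTV normalisation and non-functional constraints already in the protocol.
- Report paired differences with 95% CIs for PTV coverage, physical MLD and V20, and esophagus, heart and spinal cord dose, beside fVx and fMLD.
- Do the same for the comparison of number and timing of adaptations.

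The plans will exist anyway and no patient procedure changes, so the cost is SAP wording and extra dose-volume columns. The downside is a longer table and possibly a less favourable summary.
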